13.3 Study and Site Discontinuation

The Principal Investigator or Genentech has the right to terminate this study at any time. Reasons for terminating the study may include, but are not limited to, the following:

The incidence or severity of AEs in this or other studies indicates a potential health hazard to patients.

Patient enrollment is unsatisfactory.

Genentech will notify the investigator if Genentech decides to discontinue the study.

The Principal Investigator has the right to close a site at any time. Reasons for closing a site may include, but are not limited to, the following:

Excessively slow recruitment

Poor protocol adherence

Inaccurate or incomplete data recording

Non-compliance with the International Conference on Harmonisation (ICH) guideline for Good Clinical Practice (GCP)

No study activity (i.e., all patients have completed and all obligations have been fulfilled)

14.0 BIOSTATISTICS

14.1 Determination of Sample Size

To accomplish our primary objectives we will use a randomized parallel 2-arm 1-stage design. All patients will be randomly assigned to one of the two treatment arms, and each arm will be monitored and analyzed separately. For both arms, a 43% or higher response rate is considered promising, whereas a 20% or lower is considered not promising.

Novel therapies [e.g. bortezomib or lenalidomide] have single agent ORR of ~20% in relapsed/refractory FL [Goy 2005, Witzig 2009, Di Bella 2010] and are highly active in combination [e.g. when combined with the anti-CD20 monoclonal antibody rituximab]. These data suggest that excluding an ORR <20% while targeting an ORR >43% would be a conservative approach to evaluation of atezolizumab treatment effect as a single agent or in combination with low dose local radiotherapy in this population of patients with relapsed/refractory FL. To this end for each arm, a total of 25 patients will be accrued (once one arm reaches the enrollment goal of 25, randomization will stop and all the future patients will be automatically assigned to the other arm).

If 8 or fewer patients in either treatment arm respond, that treatment will be considered not promising. If 9 or more patients respond in either treatment arm, then that arm will be declared promising and worthy of further investigation.

This 1-stage design has type 1 and 2 error rates at 0.05 and 0.2, respectively. Given this design we may stop either arm early if we have observed 17 or more non-responders. If both arms are declared desirable by demonstrating 9 or more responses in their 25-patient cohorts, we will use the pick-the-winner approach as a general principle where the choice of which arm will be suitable for further study will be based on the absolute number of responses. If the treatment arm with a higher number of responses is also associated with more toxicity, then the investigators will weigh both the absolute number of responses and toxicity in selecting which arm is suitable for further study. If the difference in the true response rates of the treatment arms is 10% (i.e. 43% vs 53%) then the chance that the regimen with the higher response rate will be picked is over 70%. If the difference in the true response rates of the treatment arms is 15% (i.e. 43% vs 58%) then the chance that the regimen with the higher response rate will be picked is over 80%.

14.2 Planned Efficacy Evaluations

Patients will have their response classified according to the *Lugano Classification* as outlined in Appendix 4. Patients who have received at least one cycle of therapy and the planned radiation therapy (if randomized to receive radiotherapy) will be considered evaluable for response. Patients will be monitored periodically for the primary and secondary measurements (see Appendix 4 and Appendix 5 for protocol requirements regarding required imaging modalities and reporting requirements).

14.3 Primary Efficacy Variables

Objective response is defined as a CR or PR, as determined by investigator assessment using *the Lugano Classification on Treatment Response Assessment Timepoints* (Appendix 4). Patients not meeting these criteria, including patients without any post-baseline tumor assessment, will be considered nonresponders in the analysis of objective response.

14.4 Secondary Efficacy Variables

PFS is defined as the time from the first day of study treatment to PD or death, whichever occurs first. If a patient is alive and has not experienced PD, PFS will be independently censored at the day of the last tumor assessment. Patients with no post-baseline tumor assessments will be included in the PFS analysis but censored at the start of treatment.

OS is defined as the time from the first day of study treatment to death from any cause. For OS, patients without a date of death will be independently censored on the date a patient was last known to be alive.

Incidence of toxicity and adverse events will be summarized by frequencies and percentages for each of the two cohorts.

Patients with early withdrawal from the study will be considered as independently censored according to previous paragraphs. However, the censoring may be related to the disease status and therefore not independent. Therefore, sensitivity analyses will be conducted where these patients will be counted as events.

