10.3 Follow-Up Assessments

Patients who discontinue early from treatment or who complete the study treatment period will be followed as outlined below. If disease progression is clinically suspected, this should be confirmed by radiological examination as soon as possible. For patients who are being treated beyond progression, see Appendix 4 for the frequency of imaging assessments to monitor response.

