10.4 Post-Treatment Evaluations

Patients who discontinue study treatment for reasons other than PD (e.g., toxicity) should continue to undergo the full tumor assessment 6–8 weeks after study treatment is discontinued and

every six months thereafter until the patient dies, experiences PD, withdraws consent, or until the study closes, whichever occurs first. Patients who start a new anticancer therapy in the absence of PD should continue to be followed for progression according to the protocol schedule unless consent is withdrawn, the patient dies, or the study closes, whichever occurs first.

For patients who experience PD or who discontinue the study treatment due to an AE or SAE, full tumor assessment should be obtained within 30 days after the last dose of study treatment or before another anticancer therapy is initiated. Additional required tests for these patients are outlined in Appendix 1.

Patients that drop out prior to evaluation due to PD, AE, SAE will be assessed for survival and toxicity every 3 months until the start of new anti-lymphoma therapy.

Female patients of reproductive potential who are not surgically sterile must practice adequate birth control for a minimum of twelve months post-treatment; male patients who are not surgically sterile must practice adequate birth control for a minimum of three months post-treatment.

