14.5 Method of Analysis

The best overall response is the best response recorded from the start of treatment until progression/recurrence (taking as reference for progressive disease the smallest measurements recorded since the treatment started), and is the best overall response rate at any response assessment timepoint (see Appendix 5). Objective response rates will be described for patients assigned to each treatment arm as long with exact 95% confidence intervals.

Progression-free survival, and overall survival will be calculated from the start of treatment by using the Kaplan-Meier method along with 95% confidence intervals. Patients' withdrawals from interventions for reasons other than progression or death will be treated as independent censoring, and sensitivity analyses will be conducted as described in 14.4

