14.6 Method of Analysis for Correlative Endpoints

Objective response rates, progression-free survival, and overall survival will be estimated for patients with preexisting tumor antigen restricted tumor infiltrating lymphocytes (TILs) and patients without preexisting tumor antigen restricted (TILs), and for patients who demonstrate a 2-fold expansion of T cell receptor (TCR) clonality and patients who do not demonstrate a 2-fold expansion of TCR clonality, and groups will be compared using Fisher's exact tests (ORR) and logrank tests (PFS and OS). Similar comparison will be performed to associate other biomarkers described in 2.3

with the outcomes. To assess the impact of treatment on peripheral blood cytokine/chemokine levels, Wilcoxon signed rank test will be used to test the intra-patient changes in these factors.

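### Section 14.4 censors every patient without a post-baseline scan at day 0 and does not limit this to living patients, so a death before any scan would not count as a PFS event

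*Combined protocol and SAP*

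**What the plan says.** Three consecutive sentences of section 14.4 govern PFS.

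- The definition: "PFS is defined as the time from the first day of study treatment to PD or death, whichever occurs first".
- The general censoring rule: "If a patient is alive and has not experienced PD, PFS will be independently censored at the day of the last tumor assessment".
- The rule for patients without a scan: "Patients with no post-baseline tumor assessments will be included in the PFS analysis but censored at the start of treatment".

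Later in 14.4, the plan turns to withdrawals: "Patients with early withdrawal from the study will be considered as independently censored according to previous paragraphs". It accepts that this censoring may be informative and adds a sensitivity analysis that counts these patients as events. OS in 14.4 counts death from any cause and sets no scan condition. Section 14.3 counts patients without a post-baseline assessment as nonresponders.

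On timing, Appendix 5 lists the first on-treatment response assessment at C5D1. The Appendix 1 flowsheet also marks tumor assessment in the column that begins with Cycles 3, 4 and 6.

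**The concern.** The second sentence carries the condition that the patient is alive and free of progression; the third does not. A patient who dies before any post-baseline scan is therefore an event under the definition and a day-0 censoring under the third sentence. Nothing in the plan says which prevails.

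Such deaths can be observed. Section 10.4 foresees patients who drop out before evaluation because of progression or adverse events and follows them for survival. Section 11.4 requires deaths in the adverse-event reporting period to be reported.

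If the third sentence is followed, an observed PFS event is discarded and the patient adds nothing to the estimate. Two analysts could also code the same death differently, each with support in 14.4. In an open-label trial that choice should be settled before the data are seen.

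**Working it through.** **The rules side by side, for a patient who dies before any post-baseline scan**

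| Rule | Result |
|---|---|
| 14.4, PFS definition | Event on the date of death |
| 14.4, general censoring rule | Does not apply (patient not alive) |
| 14.4, no-scan rule, as written | Censored at day 0 |
| 14.4, OS | Event on the date of death |
| 14.3, response | Nonresponder |

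Only PFS can lose this patient.

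**When it can happen.** With 21-day cycles, C5D1 falls on day 1 + 4 × 21 = 85. If the flowsheet mark at Cycle 3 is taken at face value, a scan could come on day 1 + 2 × 21 = 43. Note e of the flowsheet refers to Appendix 5 for imaging requirements, and Appendix 5 starts at C5D1. The conflict does not depend on which is right, because any death before a first scan triggers it.

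**Stated figures.** The plan gives no PFS target or power, so there is no PFS figure to reproduce. Its design figures concern response (14.1: 25 per arm, 9 or more responses, 20% against 43%). Exact binomial calculation gives a type 1 error of 0.0468 and power of 0.818, in line with the stated 0.05 and 0.2. The PFS rule does not enter that calculation.

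**Size of the effect.** Inputs: n = 25 per arm (14.1); k deaths before any scan (assumed, since the documents give no rate); no other censoring (assumed). Let S be the event-free proportion among the other 25 − k patients at a time after those k deaths.

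- No-scan rule as written: Kaplan-Meier PFS = S.
- Deaths counted as events: PFS = S × (25 − k)/25.
- Difference: S × k/25. Since S is at most 1, this is at most 1/25 = 4.0 points per death.

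Example with 10 of 25 patients event-free at 12 months (assumed):

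| k | Deaths counted | No-scan rule as written | Difference |
|---|---|---|---|
| 0 | 10/25 = 40.0% | 10/25 = 40.0% | 0 |
| 1 | 10/25 = 40.0% | 10/24 = 41.7% | 1.7 points |
| 2 | 10/25 = 40.0% | 10/23 = 43.5% | 3.5 points |
| 3 | 10/25 = 40.0% | 10/22 = 45.5% | 5.5 points |

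The 4-point maximum occurs when nothing else has happened. At week 12, with one such death and no other event, PFS is 24/25 = 96% if the death counts and 100% under the rule as written.

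**How often.** At assumed rates of 1%, 2% or 4% per patient, the chance of no such death in an arm of 25 is 0.99^25 = 78%, 0.98^25 = 60% or 0.96^25 = 36%. Averaging 10/(25 − k) − 0.40 over the binomial distribution of k gives a mean shift of 0.4, 0.9 or 1.7 points. For scale, the exact 95% confidence interval for 10/25 is 21% to 61%.

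**The case against.** The best reply is that context settles the matter. Death is already an event under the definition, and the general rule covers living patients. The third sentence may then only supply the date that the general rule cannot give when no assessment exists. Section 14.5 leans the same way: "withdrawals from interventions for reasons other than progression or death will be treated as independent censoring". That reading is plausible, and the point does not claim that the sponsor means to discard early deaths. But 14.5 speaks of withdrawal from the intervention, not of deaths without a scan, and the third sentence is written for all patients without one. The missing limit remains.

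The sensitivity analysis helps in part. A patient who drops out before evaluation and then dies may well be an early withdrawal, and would be counted as an event there. A patient who dies on study is not clearly a withdrawal, and the main PFS analysis stays as written for both.

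The group is also small. Section 10.3 says: "If disease progression is clinically suspected, this should be confirmed by radiological examination as soon as possible". For patients with progression or an adverse-event stop, 10.4 adds: "full tumor assessment should be obtained within 30 days after the last dose of study treatment or before another anticancer therapy is initiated". The flowsheet marks an off-treatment tumor assessment too, and entry requires ECOG 0 or 1. All of this stands, and it is why the point is minor.

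A reader might infer that every death up to day 99 is lost, by adding 14 days to C5D1. The documents do not support that. The 14-day note in Appendix 1 is attached to the column for Cycles 3, 4, 6 and onward, not to Cycle 5, and Appendix 5 prints that window only for C9D1 and C13D1. Earlier scans are also possible.

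**Conclusion.** The concern holds as a minor defect. Applied as written, the no-scan sentence contradicts the PFS definition in the same section, and no other section clearly corrects it. The later PFS estimate rises by at most 4 points per early unscanned death in an arm of 25. That bound assumes no other censoring and refers to times after the deaths. With no such death there is no effect. The number of such deaths is unknown, so the examples and rates above are illustrations, not predictions.

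A reader might infer that the trial's main conclusion is at risk. It is not: the response rule counts these patients as nonresponders, OS counts their deaths, and PFS is a secondary endpoint estimated per arm without a hypothesis or power calculation. What is exposed is the PFS estimate and the logrank comparisons of PFS between biomarker groups in 14.6.

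**What to change.** In 14.4, limit day-0 censoring to patients who are alive, have no documented progression and have no post-baseline tumor assessment. Add that a death before the first post-baseline assessment is a PFS event on the date of death. No change to 14.5 or to the follow-up sections is needed to repair this.

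The cost is wording only. Sample size, scan schedule, the response rule and the OS analysis stay as they are. If such deaths occur, the reported PFS may be slightly less favourable than under the sentence as it stands.

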11.1.1 Adverse Events

All AEs (including SAEs and protocol-defined events of special interest [see Section 6.2]), regardless of attribution, will be recorded until 30 days after the last dose of study treatment, until study discontinuation/termination, or until initiation of subsequent anticancer therapy, whichever occurs first. After this period, investigators should report only those AEs (including pregnancy-related AEs) considered related to prior study treatment. Ongoing AEs considered related to study treatment will be followed until one of the following conditions is met: the event has resolved to baseline grade, the event is assessed by the investigator as stable, new anticancer treatment is initiated, the patient is lost to follow-up, the patient withdraws consent, or it has been determined that study treatment or participation is not the cause of the AE.

See the Schedule of Assessments provided in Appendix 1 for specified follow-up assessments.

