12.1.4 Safety Outcome Measure

Nature, frequency, severity, and timing of adverse events.

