16.2.1 Monitoring

Safety will be evaluated in this study through the monitoring of all serious and non-serious AEs, defined and graded according to NCI CTCAE v5.0. Patients will be assessed for safety (including laboratory values) according to the schedule in Appendix 1 patients will be followed for safety for 90 days following the last dose of study treatment or until receipt of another anticancer therapy, whichever comes first.

General safety assessments will include serial interval histories, physical examinations, and specific laboratory studies, including serum chemistries and blood counts (see Appendix 1 for the list and timing of study assessments). All serious adverse events (SAEs) and protocol-defined events of special interest (see Section 17.2) will be reported in an expedited fashion (see Section 17.2). In addition, the investigators will review and evaluate observed AEs on a regular basis.

Patients who have an ongoing study treatment related AE upon study completion or at discontinuation from the study will be followed until the event has resolved to baseline grade, the event is assessed by the investigator as stable, new anticancer treatment is initiated, the patient is lost to follow-up, the patient withdraws consent, or until it has been determined that study treatment or participation is not the cause of the AE.

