17.2 Serious Adverse Event (SAE) Reporting

An adverse event is considered serious if it results in ANY of the following outcomes:

Death

A life-threatening adverse event

An adverse event that results in inpatient hospitalization or prolongation of existing hospitalization

A persistent or significant incapacity or substantial disruption of the ability to conduct normal life functions

Results in a congenital anomaly/birth defect

Is an Important Medical Event (IME) that may not result in death, be life threatening, or require hospitalization may be considered serious when, based upon medical judgment, they may jeopardize the patient or participant and may require medical or surgical intervention to prevent one of the outcomes listed in this definition

Note: Hospital admission for a planned procedure/disease treatment is not considered an SAE.

SAE reporting is required as soon as the participant starts investigational treatment/intervention.

SAE reporting is required for 30-days after the participant's last investigational

treatment/intervention. Any event that occurs after the 30-day period that is unexpected and at least possibly related to protocol treatment must be reported.

Please note: Any SAE that occurs prior to the start of investigational treatment/intervention and is related to a screening test or procedure (i.e., a screening biopsy) must be reported.

All SAEs must be submitted in PIMS. If an SAE requires submission to the HRPP office per IRB SOP RR-408 'Reporting of Serious Adverse Events', the SAE report must be submitted within 5 calendar days of the event. All other SAEs must be submitted within 30 calendar days of the event.

The report should contain the following information:

The date the adverse event occurred

The adverse event

The grade of the event

Relationship of the adverse event to the treatment(s)

If the AE was expected

Detailed text that includes the following

- An explanation of how the AE was handled
- A description of the participant's condition
- Indication if the participant remains on the study

If an amendment will need to be made to the protocol and/or consent form

If the SAE is an Unanticipated Problem

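### The crude adverse-event percentages in 14.4 ignore unequal time under observation, so they tend to show more affected patients in the longer-treated arm, and 14.1 lets an undefined excess of toxicity count against the arm with more responses

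*Combined protocol and SAP*

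**What the plan says.** Section 14.4 gives the whole adverse-event analysis in one sentence: "Incidence of toxicity and adverse events will be summarized by frequencies and percentages for each of the two cohorts". Section 12.1.4 defines the safety outcome more widely, as "Nature, frequency, severity, and timing of adverse events", but section 14 has no analysis of timing.

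Three passages describe how long events are collected:

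- 11.1.1: all events, "regardless of attribution, will be recorded until 30 days after the last dose of study treatment", or until study discontinuation or new anticancer therapy if that comes first. It continues: "After this period, investigators should report only those AEs (including pregnancy-related AEs) considered related to prior study treatment".
- 16.2.1: "patients will be followed for safety for 90 days following the last dose of study treatment or until receipt of another anticancer therapy", whichever is first.
- 17.2, for serious events: "Any event that occurs after the 30-day period that is unexpected and at least possibly related to protocol treatment must be reported".

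Time on drug is set by 4.2 (21-day cycles, up to 17), 9.3 (treatment continues while the investigator sees benefit) and 13.2 (treatment stops at progression, with an exception for suspected pseudoprogression).

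Section 14.1 brings toxicity into the choice of arm. It applies when both arms have 9 or more responses among 25: "If the treatment arm with a higher number of responses is also associated with more toxicity, then the investigators will weigh" responses and toxicity together. It does not say how toxicity is measured.

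**The concern.** The period in which any-attribution events are recorded ends a fixed time after the last dose, and the last dose depends on progression. An arm with later progression therefore has a longer average observation period. A crude percentage takes no account of that length, so two arms with the same event rate per month would be expected to show different percentages.

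The difference matters because of 14.1. The arm with more responses will usually be the arm that stays on drug longer, and it is the arm on which the toxicity clause operates. With no measure defined, the crude table is the only planned summary available when the clause is applied. Section 14.4 does recognise, for PFS and OS, that early withdrawal may be related to disease status, and it adds sensitivity analyses. Adverse events, which are also observed for an outcome-dependent time, get none.

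**Working it through.** **The plan's own figures (14.1), exact binomial, 25 per arm, 9 or more responses.** Type 1 error at 20% is 0.0468 (stated 0.05). Power at 43% is 0.818 (stated 0.80). The better arm has strictly more responses with probability 71.6% (43% vs 53%) and 82.4% (43% vs 58%), against the stated over 70% and over 80%. All reproduce. The documents give no figure for adverse events by arm.

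**Inputs from the documents.** Dose k falls on day 1 + 21(k − 1): C4D1 = day 64, C8D1 = day 148, C17D1 = day 337. The response scans are at C5D1 (day 85) and C9D1 (Appendix 5).

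**Assumptions, because the documents give neither time on treatment nor event rates.** Responders receive all 17 doses. Non-responders stop at the C5 scan (last dose C4D1) or, alternatively, at the C9 scan (last dose C8D1). The event rate h is the same in both arms.

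**Observation window under 11.1.1.** Responder: 337 + 30 = 367 days. Non-responder: 64 + 30 = 94 days, or 148 + 30 = 178 days.

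Mean window = p × 367 + (1 − p) × 94, where p is the response rate:

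- 43%: 0.43 × 367 + 0.57 × 94 = 211 days
- 53%: 0.53 × 367 + 0.47 × 94 = 239 days
- 58%: 0.58 × 367 + 0.42 × 94 = 252 days

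**Crude incidence at a constant rate** = p(1 − e^(−367h)) + (1 − p)(1 − e^(−sh)), with s = 94 or 178. Worked case: h = 1 event per 250 days and s = 94. The two terms are 1 − e^(−1.468) = 0.770 and 1 − e^(−0.376) = 0.313.

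- 43%: 0.43 × 0.770 + 0.57 × 0.313 = 51.0%
- 58%: 0.58 × 0.770 + 0.42 × 0.313 = 57.8%

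The gap is 6.8 points, or 1.7 of 25 patients. With two independent Binomial(25) counts, the 58% arm shows more affected patients with probability 0.64 and fewer with 0.26. With equal crude risks the two probabilities are 0.44 each.

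**Range of the spurious excess, in percentage points:**

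| Assumption | 43% vs 53% | 43% vs 58% |
|---|---|---|
| Constant rate 0.2 to 4 per year, stop at C5 scan | 1.3 to 4.7 | 2.0 to 7.0 |
| Same rates, stop at C9 scan | 0.9 to 2.6 | 1.3 to 3.9 |
| 90-day tail (16.2.1), rate 0.5 to 2 per year, stop at C5 scan | 2.5 to 3.5 | 3.8 to 5.2 |
| All events in the first 94 days | 0 | 0 |

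**Stable disease.** Section 3.1 reports 3 of 14 follicular patients responding and 6 more with stable disease after cycle 4 of an atezolizumab–obinutuzumab combination. That is 6 of 11 non-responders not yet progressed. If 6/11 of non-responders stay on drug in the worked case, the 6.8 points fall to 5.2 (they stop at the C9 scan) or 3.1 (they complete 17 cycles).

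**Calibrated to 3.3.2.2.** Choosing h so that the model's 43% arm matches the single-agent study's 93.2% (any event) or 11.8% (related Grade 3–4) gives gaps of 1.8 and 2.2 points for 43% vs 58%, about half a patient of 25. Events of middling frequency give the larger gaps.

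**What the alternatives do.** At a constant rate of 1 per year, the rate per patient-year is 1.00 in both arms and cumulative incidence at day 94 is 22.7% in both. If all events come early, however, the same number of events over 252 rather than 211 days makes the overall rate in the longer-treated arm 1 − 211/252 = 16% lower. A single exposure-adjusted rate then errs in the opposite direction.

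**The case against.** A reader might infer that adverse events are collected only to day 30. They are not. Related events remain reportable under 11.1.1, unexpected and possibly related ones under 17.2, and 16.2.1 gives 90 days. Section 10.4 adds three-monthly toxicity checks for some early drop-outs, and Appendix 1 marks adverse events at follow-up visits. This narrows the point but does not remove it: the longer-treated arm also has more drug exposure, and 10.5 restricts follow-up after progression to survival and new therapy.

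A reader might also infer that 14.1 formally compares the 14.4 percentages. It does not cite them, 14.4 only summarises, and 14.1 says the arms are analysed separately. The clause leaves the matter to investigator judgement, and severity and timing are also recorded under 12.1.4. The fair criticism is that toxicity is undefined and only one summary is planned.

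Nor is the arm with more responses longer-observed by necessity. Exposure follows progression, patients with stable disease stay on drug, and stopping for toxicity shortens the window in either arm.

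Finally, a constant rate is an assumption. Appendix 8 places influenza-like illness mainly 1 to 2 weeks after the first cycle and infusion reactions in cycles 1 and 2, and radiotherapy is given on days 2 and 3. For such events the artefact is nil. Crude tables are also ordinary in a descriptive phase II of this size. All of this limits the size and certainty of the effect; none of it makes the crude percentage a sound basis for comparing arms with different time on drug.

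**Conclusion.** The point holds as a tendency of modest size. All-attribution recording follows time on drug, time on drug follows progression, and the only planned summary ignores it. At equal event rates the crude table therefore tends to favour the shorter-treated arm. For 43% vs 58% response the excess is about 0 to 7 percentage points, under 2 of 25 patients. The upper end needs a roughly constant event rate of middling frequency and non-responders who stop at the C5 scan; early events or prolonged stable disease bring it down, to nil if all events fall in the first cycles. For scale, the expected response advantage in 14.1's own scenarios is 0.10 × 25 = 2.5 or 0.15 × 25 = 3.75 patients, so an artefact of one or two patients could affect a close choice. The stronger reading, that the better arm is bound to look more toxic and be rejected, is not supported. This is a cheap improvement worth making before results are seen, because a toxicity measure settled later would be chosen with the leading arm already known.

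**What to change.** In 14.4, keep the crude table and add for each arm:

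- (a) the proportion of patients with any-grade and with Grade 3 or higher adverse events from C1D1 to C5D1, counting every event recorded in that common window whether or not treatment has stopped, with deaths shown separately. Stops for progression should not be handled as competing events, since that would lower the apparent incidence in the arm that progresses more.
- (b) time on treatment, and adverse-event rates per patient-month, split into C1–C4 and C5 onward so that a falling rate does not favour the longer-treated arm.

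In 14.1, state that toxicity in the selection clause is judged mainly on (a), with (b) and the crude table as support. Reconcile the 30 days of 11.1.1 with the 90 days of 16.2.1, so that the period behind every denominator is defined.

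The cost is wording and a few tables from dates already recorded, with no new visits. Three limits should be stated. Estimates are imprecise at 25 per arm. Table (a) alone misses late immune events, which (b) covers. Under the 30-day rule, a patient whose last dose is C4D1 is covered to day 94, past C5D1 on day 85, but one whose last dose is C3D1 (day 43) is covered only to day 73; the number with incomplete coverage should be reported per arm.
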